10.5.3 Safety analyses

Safety endpoints include death through three months, SAEs, discontinuation of study infusions, and severe AEs. These events will be analysed univariately and as a composite endpoint. Time-to-event methods will be used for death and the composite endpoint. Each AE will be counted once for a given participant and graded by severity and relationship to COVID-19 or study intervention. AEs will be coded using the current version of the Medical Dictionary for Regulatory Activities (MedDRA). AEs will be presented by system organ class, duration (in days), start- and stop-date. Adverse events leading to premature discontinuation from the study intervention and serious treatment-emergent AEs should be presented either in a table or a listing.

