2.3 Study design

The NOR-SOLIDARITY study is an adaptive, randomized, open clinical multicentre trial to evaluate the safety and efficacy of possible therapeutic agents in hospitalized adult patients diagnosed with COVID-19. See the WHO COVID-19 core protocol (Appendix 1) for the core trial design. This multicentre add-on trial will follow the WHO core protocol version 10 dated 22.03.2020 but will add additional secondary and exploratory endpoints.

Adults (age ≥ 18 years) recently hospitalized, or already in hospital, with definite COVID and, in the view of the responsible doctor, no contra-indication to any of the study drugs will be randomly allocated between

- Local standard of care alone,
OR local standard of care plus
- Remdesivir (one intravenous loading dose, then daily infusions for altogether 10 days)

The primary objective of the trial is to investigate the effect of Remdesivir on all-cause in-hospital mortality compared to standard of care.

Patients will be followed daily during hospitalization, after 28 days by telephone/sms and then by an outpatient clinical visit after 3 months.

In the core protocol follow-up data are only collected at discharge. In this protocol subjects will additionally be assessed for efficacy and safety both during hospitalization and after hospitalization.

In addition to the global independent data and safety monitoring board (DSMB) as described in the core protocol, a national DSMB will monitor the safety and risk-benefit of the trial interventions in the Norwegian population.

[figure not shown]

Figure 2: The Investigational NOR-SOLIDARITY protocol

3 Objectives and endpoints

Objectives	Endpoints (Outcome measures)
Primary (in line with WHO core protocol)	
To investigate the effect of Remdesivir on all-cause in-hospital mortality compared to standard care.	All-cause in-hospital mortality
Secondary (in line with WHO core protocol)	
Assess the effect of Remdesivir on hospital duration, receipt of ventilation or intensive care, and to identify any serious adverse reactions.	During hospitalization 
 • Receipt of mechanical ventilation • Time to first receiving and duration of mechanical ventilation • Receipt of intensive care • Duration of intensive care • Occurrence of Suspected Unexpected Serious Adverse Reactions (SUSARs)
Secondary (as addition to the WHO core protocol)	

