Assess the effect of Remdesivir on 28 days mortality, viral clearance, kidney and myocardial failure, co-infections, organ dysfunction and health-related Quality of Life.	Assessed during hospitalization 
 • Viral clearance as assessed by SARS-CoV-2 PCR in oropharyngeal specimens during hospitalization • Occurrence of kidney failure (eGFR <40 mL/min) • Occurrence of myocardial involvement assessed by biochemical markers as well as echocardiography measuring left ventricular ejection fraction within the first week • Occurrence of co-infections (super infections with bacteria, fungi and other virus) Assessed after 28 days 
 • Overall survival • Patient reported respiratory health status by CAT (Chronic Obstructive Pulmonary Disease (COPD) assessment Test) score Assessed after 3 months 
 • Occurrence of systolic and diastolic cardiac dysfunction and level of remodelling assessed by echocardiography and biochemical markers • Occurrence of pulmonary dysfunction and level of fibrosis assessed by spirometry and thoracic CT scan • Health related quality of life assessed by the RAND 36-item Short Form Health Survey (SF-36) item scores and the 5-dimension EuroQol (EQ-5D) questionnaires index value.
Exploratory (as addition to the WHO protocol)	

Assess the effect of Remdesivir on biomarkers and its safety.	Biomarkers during hospitalization and after 3 months 
 • Inflammatory and anti-inflammatory mediators as assessed in serum and plasma • Markers of extracellular matrix remodelling • Markers of endothelial activation • Markers of platelet activation • Cellular immunity • Prognostic biosignatures (RNA) • Gut microbiota assessed by rectal swab • Pharmacokinetics during hospitalization • Adverse events during hospitalization
---	--

4 Study population

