10.3 Population for Analysis

The following populations will be considered for the analyses:

- Intention to treat (ITT) population: All randomized participants will be included in the main ITT analyses, regardless of protocol adherence.
- Per-protocol population (PP): Includes all patients in the ITT population having completed the study treatment without major protocol violations and good adherence to the IMP.

Criteria for inclusion in the PP population will be specified in the SAP and the final criteria will be defined prior to database lock

- Safety population: Includes all subjects with any safety information after baseline. Patients randomized to Remdesivir without receiving any amount of the treatment will be excluded from the safety population.
- Total population: All enrolled participants independent of study arm will be used for additional analyses in the total population.

The primary population is the ITT population.

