10.5.2 Secondary analyses

Between group comparisons will be performed for the primary variable on the per-protocol population in addition to secondary efficacy endpoints on both efficacy populations (ITT and PP populations).

The between-group comparisons for secondary variables will be tested as for the primary variable where applicable and additional analyses will be performed based on the following methods (but not limited to):

- Continuous secondary variables will be subject to repeated measures mixed models or appropriate non-parametric alternatives
- Binary response variables will be analysed using logistic regression (possibly adjusting for within-subject dependencies by generalized estimating equations or mixed models) or chi-square/Mantel-Haenszel tests
- Time-to-event variables will be analysed using the Kaplan-Meier method and comparisons between the two groups will be performed using the log rank test, Cox regression analyses or appropriate parametric models such as the gamma or Weibull model.

Unless otherwise specified, all statistical hypotheses will be tested as the primary variable, i.e. with an assessment of superiority of the estimated difference between the groups. All efficacy analyses will be presented with the results from the hypothesis testing (by p-value) in addition to estimates and 95% confidence limits of the treatment effect.

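### The safety composite counts stopped study infusions, an event only the remdesivir arm can have, so a between-arm comparison of it can be biased towards harm

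*Protocol*

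**What the plan says.** Section 10.5.3 of the protocol lists the safety endpoints: "Safety endpoints include death through three months, SAEs, discontinuation of study infusions, and severe AEs". It continues: "These events will be analysed univariately and as a composite endpoint". On method it says: "Time-to-event methods will be used for death and the composite endpoint".

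Section 2.3 gives the control arm as "Local standard of care alone". The other arm adds a loading dose and daily infusions, 10 days in all. Sections 10.2.2 and 10.2.3 describe the trial as open label, and no placebo is mentioned.

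Infusions may end for several reasons. Section 6 lets patients leave study treatment at any time and remain in the study. Section 9.4 leaves the local doctor free to discontinue study medication. Section 5.2 asks that discontinuation be considered after a large fall in eGFR.

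On the safety population, section 10.3 says: "Patients randomized to Remdesivir without receiving any amount of the treatment will be excluded from the safety population". It sets no matching condition for standard care.

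**The concern.** A composite compared between randomised arms needs components that can occur in both. Stopping an infusion cannot occur under standard care alone, so this component can only add events to the remdesivir arm. The direction of any bias is fixed by the definition, before any data are seen.

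The stops that matter are those with no earlier death, SAE or severe AE, such as a patient's choice or a doctor's decision. They need not reflect harm, yet a first-event analysis counts each of them on a par with a death. This is the only safety composite the protocol specifies. A reader could take an excess in it as evidence against the drug when part or all of it comes from the definition.

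**Working it through.** **Is the composite compared between arms?** Section 10.5.3 does not say so outright. Three places point that way. The trial has two arms. The objectives table (section 3) includes "Assess the effect of Remdesivir on biomarkers and its safety". For time-to-event variables, section 10.5.2 says "comparisons between the two groups will be performed using the log rank test, Cox regression analyses or appropriate parametric models", although that text concerns secondary variables. The comparison is a strong inference, not stated text.

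**Arm size.** The protocol gives no figure for the composite, so I use its recruitment goal (section 10.1). That goal reproduces. For 26% versus 16%, two-sided 2.5% and 90% power, the unpooled formula gives (2.2414 + 1.2816)² × (0.26×0.74 + 0.16×0.84) / 0.10² = 12.411 × 0.3268 / 0.01 = 405.6, hence 406 per arm.

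**Model for a harmless drug.** Both inputs below are assumptions, because the protocol states neither:
- q = share of patients with death, SAE or severe AE, the same in both arms
- d = share of otherwise event-free remdesivir patients who stop infusions

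The composite rate is q under standard care and p = q + (1 − q)d under remdesivir. With n per arm and p̄ = (p + q)/2, the chance of a significant excess at two-sided 5% is Φ[(p − q − 1.96·s₀)/s₁], where s₀ = √(2p̄(1 − p̄)/n) and s₁ = √((p(1 − p) + q(1 − q))/n).

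Worked case, q = 25%, d = 8%, n = 406:
- p = 0.25 + 0.75×0.08 = 0.310
- s₀ = √(2×0.28×0.72/406) = 0.0315
- s₁ = √((0.2139 + 0.1875)/406) = 0.0314
- (0.060 − 1.96×0.0315)/0.0314 ≈ −0.06, so the probability is about 0.48

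| n per arm | q | d | Composite, remdesivir v. standard care | P(false significant excess) |
|---|---|---|---|---|
| 406 | 25% | 0% | 25.0% v. 25% | 2.5% (nominal) |
| 406 | 25% | 2% | 26.5% v. 25% | about 7% |
| 406 | 25% | 5% | 28.75% v. 25% | about 23% |
| 406 | 25% | 8% | 31.0% v. 25% | about 48% |
| 406 | 25% | 10% | 32.5% v. 25% | about 66% |
| 406 | 50% | 2% | 51.0% v. 50% | about 5% |
| 406 | 50% | 5% | 52.5% v. 50% | about 11% |
| 100 | 25% | 8% | 31.0% v. 25% | about 15% |

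The row with 100 per arm is an assumed shortfall. Section 12 warns that enrolment may be too low, and section 10.4 allows analysis once the global trial stops.

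**Check by log-rank test.** I simulated 3000 trials per scenario with 406 per arm, 90 days of follow-up, other events at exponential times with mean 10 days, and stops spread evenly over days 1 to 10. At q = 30% the formula gives 19% for d = 5% and 56% for d = 10%; the simulation gives 20% and 60%. The simulated figures run slightly higher because a stop also brings forward the first event of a patient who would have had one later. With d = 0 the simulated rate was 2.1% to 2.7%, so removing the component removes the bias.

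**The case against.** The strongest reply is that the bias is conditional. A stop adds a first event only in a patient with no earlier component event. Section 6 requires a stop on suspicion of a life-threatening reaction, which already counts as an SAE under section 9.1.2. A reader might infer that the composite will show harm even if the drug is harmless; the protocol does not support that, because the excess vanishes if every stop follows another component event. Stops by choice or by the doctor's decision are plainly allowed, though, so the asymmetry is not removed.

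Second, a reader might infer that the safety analysis as a whole fails to measure harm. It does not follow. The same section analyses the events one by one, so death, SAEs and severe AEs each keep a comparison free of this component. It also has AEs leading to discontinuation tabled or listed. The primary in-hospital mortality analysis is untouched, safety is largely an exploratory objective, and no stopping rule rests on the composite.

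Third, the SAP, which is not shown, may define which stops count. A narrower definition would shrink the bias, but any definition that keeps the component still has no counterpart under standard care.

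Fourth, a reader might see the safety population as a second serious bias, this time in favour of remdesivir. It is minor. Section 5.1 gives the first dose at inclusion, so little time remains for events before dosing. Both arms need some safety information after baseline. In-hospital death is already compared by intention to treat.

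**Conclusion.** The point holds in a limited form. The protocol itself fixes a composite with a component that can occur in one arm only, and nothing in it corrects this. A between-arm comparison of the composite is therefore biased towards harm whenever some remdesivir patients stop infusions without an earlier component event.

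The direction is certain; the size is not. Under the assumed rates, the chance of a false significant excess runs from about 5% to about 66%, against 2.5% nominal. It rises with the share of event-free stops and falls with a higher base rate or fewer patients. These figures also assume that the composite is tested between arms at two-sided 5%, which is inferred. The matter should be fixed, but it does not threaten the trial's main conclusion.

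**What to change.** In section 10.5.3, and in the SAP to match, limit the between-arm composite to death through three months, SAEs and severe AEs. Report stopped infusions, with reasons, descriptively for the remdesivir arm only. The table or listing of AEs leading to discontinuation can stay as it is, so no safety information is lost.

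As a minor addition, show three-month death and SAEs by allocated arm in all randomised patients beside the safety-population results, because section 10.3 drops undosed patients from one arm only. The difference is probably small.

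The cost is a wording change in the protocol and SAP plus one extra table. No new data and no further patients are needed.

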10.5.4 Descriptive statistics

Descriptive statistics will be presented with number and percentages for categorical variables, and means, standard deviation, and range for continuous variables. In case of clearly skewed continuous variables, they will be presented with median, interquartile range (25th and 75th percentiles) and range. Demographics and baseline characteristics will be presented with descriptive statistics without any hypothesis testing.

10.5.5 Missing data

If missing data is regarded as having a significant effect on the conclusions of the trial, sensitivity analyses with different methods for handling missing data will be included. Such methods may include complete case analyses, last observation carried forward, worst case/best case imputation and multiple imputation techniques.

11 Ethical considerations

This study will be conducted in compliance with the principles set out in the Declaration of Helsinki. Where applicable, the principles of Good Clinical Practice (ICH 1996) and other applicable regulations and guidelines will be used to guide procedures and considerations. This protocol will be reviewed and approved by the regional ethical committee and by The Norwegian Medicines Agency (using the EudraCT form) before patients are enrolled in the study.

After approval the study will immediately be registered in ClinicalTrials.gov.

This study is conducted during a disease outbreak. This is a challenging research situation because this falls in the area between clinical care, public health and clinical research (WHO Ethical Review in Disease Outbreak Expert Meeting 2009). Normally research activities are defined by anything conducted outside standard clinical care. The patients included in this study will be treated according to normal practice at the different hospitals, which follow international guidelines in relation to sepsis and ARDS (10, 11).

11.1 Informed Consent

Recruitment of critically ill patients who are not able to consent is a ubiquitous problem in acute and critical care research and there is a clear legal framework under which these patients may be recruited to research studies. In all cases, efforts will be made to obtain informed consent from patients early in the course of illness, before critical illness interferes with their capacity to make decisions and to confirm consent at the earliest point in recovery. Consent forms will be provided in Norwegian or in English if required. If the patient consents in participating in this add-on study he or she automatically consents in participating in the WHO global study.

In this peculiar situation with COVID 19 infected patients, the signed form may itself be a source of infection. To overcome this, a third person (health worker, nurse or physician) will be present while the patient is informed, and independently evaluate and confirm whether the patient is consent competent and voluntary says yes/no to join the study. This will thereafter be

documented in the patient's medical record. Thus, a written consent is not required as long as we ensure and document that the patient has been thoroughly informed and voluntary consents to participate.

Due to the patient condition, it is likely that he/she is not capable to sign an informed consent form. Thus, when the patient lacks the capacity to consent to participation, an appropriate representative will be approached. A pdf-file of the consent form will be sent to the patient's representative for reading, who will thereafter be contacted by phone. A third person (health worker, nurse or physician) will join this conversation, and independently evaluate and confirm whether the representative on behalf of the patient, provides an informed consent and voluntary says yes/no to join the study. This will thereafter be documented in the patient's medical record. Staff trained in consent procedures that protect the rights of the patient, and adhere to the ethical principles within the Declaration of Helsinki will be used. Staff will explain the details of the study to the participant or representative and allow them time to discuss and ask questions. The staff will review the informed consent form with the person giving consent and endeavor to ensure understanding of the contents, including study procedures, risks, benefits, the right to withdraw and alternatives to participation. Patient autonomy to withdraw from the study at any time will be respected.

We are sensitive to the fact that some patients or their representatives may feel under an unusually strong moral obligation to participate given the nature of this research and the wide, and often inaccurate, publicity surrounding emerging infections. In view of this, we have tried to make both the potential benefits and limitations of this explorative investigational study clear in the information sheet. In the informed consent form we also stress that participation is entirely voluntary and there is no penalty of any kind for declining to join the study. Balance between public health and research. Patients with emerging infections are commonly the subject of public health investigations. The work proposed here is research and will be clearly presented as such. There is no primary gain to the patient from participating. In designing and describing this research we are clear that, in accordance with the guiding principles of Good Clinical Practice, the needs and autonomy of the individual are paramount and the potential benefits to wider society do not take precedence.

11.2 Confidentiality

Clinical staff will conduct this study and those involved in the study will ensure that each study participant's privacy and confidentiality is maintained. Participants will not be identified in any published reports of this study. All records will be kept confidential to the extent provided by international and local law. All laboratory specimens, evaluation forms, reports, study protocol, documentation, data and all other information generated will be held in strict confidence. No information concerning the study or the data will be released to any unauthorized third party. Paper and electronic medical records may be accessed during the study to confirm, verify or complete clinical information provided in the case report form. Site files will at all times be accessible only to clinical and research staff. Consent will be sought for investigators to access patient data.

Participation in international collaboration involving sharing of data from the NOR-SOLIDARITY trial and merging of NOR-SOLIDARITY data with other (similar) studies will be based on fully de-identified data.

12 Scientific and peer review

The results of the study will be published in a peer-reviewed internationally recognized journal. We are aware that there may be too few patients enrolled in the study, thus our national study

may not be able to answer the objectives of the protocol. However, the principal investigators will keep close collaboration with WHO (WHO adaptive master protocol on Clinical Trial of the Safety and Efficacy of Investigational Therapeutics for the Treatment of COVID-19 in Hospitalized Patients) making it likely that the results can be incorporated in a multinational study. This will secure that the data from this study will be used in a bigger setting and contribute to increased knowledge.

13 References

1. WHO. Global Influenza Strategy 2019-2030 2019.

Appendix

A1 The WHO COVID-19 core protocol, version 10

This is attached as a separate document

A2 WHO Standard Operating Procedures and appendix, version 10

This attached as a separate document

A3 Sofa Score

Table 1. Sequential [Sepsis-Related] Organ Failure Assessment Score^a

System	Score				
	0	1	2	3	4
Respiration					
PaO ₂ /Fio ₂ , mm Hg (kPa)	≥400 (53.3)	<400 (53.3)	<300 (40)	<200 (26.7) with respiratory support	<100 (13.3) with respiratory support
Coagulation					
Platelets, ×10 ³ /μL	≥150	<150	<100	<50	<20
Liver					
Bilirubin, mg/dL (μmol/L)	<1.2 (20)	1.2-1.9 (20-32)	2.0-5.9 (33-101)	6.0-11.9 (102-204)	>12.0 (204)
Cardiovascular					
MAP ≥70 mm Hg	MAP <70 mm Hg	Dopamine <5 or dobutamine (any dose) ^b	Dopamine 5.1-15 or epinephrine ≤0.1 or norepinephrine ≤0.1 ^b	Dopamine >15 or epinephrine >0.1 or norepinephrine >0.1 ^b	
Central nervous system					
Glasgow Coma Scale score ^c	15	13-14	10-12	6-9	<6
Renal					
Creatinine, mg/dL (μmol/L)	<1.2 (110)	1.2-1.9 (110-170)	2.0-3.4 (171-299)	3.5-4.9 (300-440)	>5.0 (440)
Urine output, mL/d				<500	<200

Abbreviations: Fio₂, fraction of inspired oxygen; MAP, mean arterial pressure; PaO₂, partial pressure of oxygen.

^a Adapted from Vincent et al.²⁷

^b Catecholamine doses are given as μg/kg/min for at least 1 hour.

^c Glasgow Coma Scale scores range from 3-15; higher score indicates better neurological function.

A4 Clinical Frailty Scale

Clinical Frailty Scale*

 
1 Very Fit – People who are robust, active, energetic and motivated. These people commonly exercise regularly. They are among the fittest for their age.
	 
7 Severely Frail – Completely dependent for personal care, from whatever cause (physical or cognitive). Even so, they seem stable and not at high risk of dying (within ~ 6 months).

 
2 Well – People who have no active disease symptoms but are less fit than category 1. Often, they exercise or are very active occasionally, e.g. seasonally.
	 
8 Very Severely Frail – Completely dependent, approaching the end of life. Typically, they could not recover even from a minor illness.

 
3 Managing Well – People whose medical problems are well controlled, but are not regularly active beyond routine walking.
	 
9. Terminally Ill - Approaching the end of life. This category applies to people with a life expectancy <6 months, who are not otherwise evidently frail

 
4 Vulnerable – While not dependent on others for daily help, often symptoms limit activities. A common complaint is being "slowed up", and/or being tired during the day.
	
Scoring frailty in people with dementia
 
The degree of frailty corresponds to the degree of dementia. Common symptoms in mild dementia include forgetting the details of a recent event, though still remembering the event itself, repeating the same question/story and social withdrawal.
 
In moderate dementia, recent memory is very impaired, even though they seemingly can remember their past life events well. They can do personal care with prompting.
 
In severe dementia, they cannot do personal care without help.

 
5 Mildly Frail – These people often have more evident slowing, and need help in high order IADLs (finances, transportation, heavy housework, medications). Typically, mild frailty progressively impairs shopping and walking outside alone, meal preparation and housework.
	
* 1. Canadian Study on Health & Aging, Revised 2008. 2. K. Rockwood et al. A global clinical measure of fitness and frailty in elderly people. CMAJ 2005;173:489-495.
 
© 2007-2009, Version 1.2. All rights reserved. Geriatric Medicine Research, Dalhousie University, Halifax, Canada. Permission granted to copy for research and educational purposes only.
 
 
6 Moderately Frail – People need help with all outside activities and with keeping house. Inside, they often have problems with stairs and need help with bathing and might need minimal assistance (cuing, standby) with dressing.
	

A5 Preparation of plasma and serum (study samples)

EDTA-plasma (12 mL blood): Collect EDTA-blood into two tubes. Immediately after sampling, mix blood by inverting the tube three times. Place the tube on crushed ice (optional) and centrifuge as soon as possible (within 30 minutes, latest within 60 minutes) at 3000g for 15 minutes. Isolate plasma (leave the 0.5 cm closest to the cell layer) into NUNC-tubes. Freeze immediately -70°C/or -80°C.

Serum (8mL blood): Collect the blood in one red topped tube. Leave it undisturbed at the bench, approximately 30 minutes until coagulation. Then centrifuge at 2000g for 10 minutes. Isolate serum (leave the 0.5 cm closest to the cell layer) into NUNC-tubes. Freeze immediately -70°C/or -80°C.

Labeling: Every nunc tubes have to be named according to study site number, patient number and sample number as described in the biobank procedure.

